## Enhanced pain control after reduction mammoplasty with bupivacaine and dexamethasone regional block

### 1) Abstract of the study

**Background:** Patients undergoing reduction mammoplasty frequently suffer significant post procedure pain at the operative site. While regional nerve block is routinely performed with bupivacaine, the effects of this are limited to the up to 8 hours of action provided by this drug. Previous studies in orthopedic and thoracic surgery patients have demonstrated that addition of dexamethasone to the perineural block prolongs the duration of analgesia. This has never been studied in the plastic surgery patient. We propose that addition of dexamethasone to the infiltration solution will prolong the duration of analgesia provided by a regional block and reduce the need for adjunct narcotic medication in the postoperative period following reduction mammoplasty.

**Methods:** Patients undergoing elective Breast Surgery at Temple University Hospital will be randomized to receive a control standard perineural block with 19-mL 0.5% bupivacaine +1mL 0.9% sterile saline or block with the experimental mixture of 19mL 0.5% bupivacaine + 1mL 4mg/mL dexamethasone solution for each breast. Primary end points will be mean pain VAS score as measured every 4 hours postoperatively and postoperative narcotic consumption data during the admission following the procedure. Secondary endpoints also observed will be anti-emetic consumption, vital signs, quality of life as assessed by SF-36 and Breast-Q questionnaires, and length of hospital stay.

### 3) IRB Review History

No previous submissions

### 5) Objectives

This study aims to evaluate the effect of the addition of dexamethasone to a standard bupivacaine nerve block following reduction mammoplasty. We propose that addition of dexamethasone to the infiltration solution will prolong the duration of analgesia provided by a regional block and reduce the need for adjunct narcotic medication in the postoperative period following reduction mammoplasty.

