### 6) Background

## Enhanced pain control after reduction mammoplasty with bupivacaine and dexamethasone regional block

Breast reduction is among the most common procedures performed by the Plastic Surgery division at Temple University Hospital. These patients are generally admitted for 23 hour observation primarily due to significant postoperative pain. Currently regional nerve block is routinely performed with bupivacaine infiltration. This provides effective immediate postoperative pain control but is limited by the 2 to 8 hour duration of action provided by this drug. These patients typically require significant amount of narcotic analgesia in the postoperative period. Exparel® (bupivacaine liposome injection) is a commercially available long acting formulation of bupivacaine however its significant cost has been deemed prohibitively high for use at this and most other institutions.

A number of studies in the anesthesia literature have demonstrated that addition of dexamethasone to bupivacaine when administered as a perineural block extends the duration of analgesia. In Bjorn, et al. (Reg Anesth Pain Med, 2016 Dec) saphenous nerve block with 10mL 0.5% bupivacaine + 1mL 0.4% dexamethasone after ankle surgery significantly extended the time to first narcotic request compared to control with bupivacaine alone. Maher, et al. (Pain Med, 2016 Jul) examine the use of both IV dexamethasone (8mg) and combination perineural dexamethasone and bupivacaine as intercostal nerve block during VATS. They demonstrate statistically significant decrease in pain at 8, 20, and 24 hours postoperatively. Other studies have obtained similar results in a variety of orthopedic and neurosurgical procedures.

A PubMed search using terms “dexamethasone” and “nerve block” did not return any studies that pertain to plastic reconstructive surgeries including but not limited to breast reduction. Additionally, searches using “breast reduction” and “nerve block” or “mammoplasty” and “nerve block” returned only 1 relevant study that examines the use of Exparel® nerve block during mastectomy (Abdelsattar 2016). Again, no studies examine methods of prolonging the duration of regional anesthesia after reduction mammoplasty

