### **f) Study Endpoints**

Primary study endpoints are average VAS pain score during hospitalization and postoperative narcotic usage during the hospitalization. Secondary endpoints are need for antiemetic therapy, length of hospitalization, and aggregate pain and quality of

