## Enhanced pain control after reduction mammoplasty with bupivacaine and dexamethasone regional block

dexamethasone to prevent post-operative nausea and vomiting. It has not been evaluated by the FDA as an adjunct to local anesthesia.

Pain VAS scores are routinely collected by nursing staff and entered into Epic. We will request pain evaluations at 4 hour intervals for study patients following surgery which will be entered into the Epic medical record. Medication administration is also captured in the electronic medical record. Study data will be gathered from the Epic electronic medical record.

Patients will be asked to complete the MD Anderson Brief Pain Inventory Short Form and both the Breast-Q or the SF-36 questionnaire at their first post-operative visit.

As previously stated, regional block with bupivacaine alone is routinely offered and provided to patients. Patients who do not consent to participate in the study will be offered a regional nerve block containing only bupivacaine. Anesthesia pain service faculty will perform the block regardless of study participation or study group.

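### Longer analgesia is half of the hypothesis, but no endpoint or planned analysis measures duration directly; time to first opioid should be a named secondary endpoint

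*Combined protocol and SAP*

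**What the plan says.** The hypothesis appears in the Abstract and in section 5 (Objectives) and has two parts: that "addition of dexamethasone to the infiltration solution will prolong the duration of analgesia provided by a regional block", and that less opioid will be needed after surgery.

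Section 10(f) states: "Primary study endpoints are average VAS pain score during hospitalization and postoperative narcotic usage during the hospitalization". The Abstract agrees, with VAS recorded every 4 hours. On the remaining endpoints the Abstract says: "Secondary endpoints also observed will be anti-emetic consumption, vital signs, quality of life as assessed by SF-36 and Breast-Q questionnaires, and length of hospital stay". Section 10(f) has a similar list, with pain and quality-of-life survey scores at the first postoperative visit.

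Section 10(i) (Data Management) plans t-tests on the endpoints and a mixed model of pain scores over time, with pain medication requirement controlled for in the model. It names no survival method.

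Section 6 (Background) gives bupivacaine a 2 to 8 hour action and treats this as the limitation to overcome. It cites an ankle-surgery study in which the combination "significantly extended the time to first narcotic request compared to control with bupivacaine alone". On data sources, section 10(g) says: "We will request pain evaluations at 4 hour intervals for study patients following surgery", and "Medication administration is also captured in the electronic medical record".

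**The concern.** The reason for the trial is that the block wears off too soon, yet nothing in the endpoint list records when it wears off. A mean or a total over the whole stay mixes hours when both blocks work with hours when only one may. The plan cites time to first opioid request as evidence of prolongation elsewhere but does not adopt that measure or any other measure of duration.

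Two things are at stake. A favourable result on mean VAS or total opioid would not directly support a statement that analgesia lasted longer. And a real prolongation that shows only in part of the stay could be averaged down to a difference the trial is unlikely to detect.

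**Working it through.** **1. Objective against endpoints**

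| Part of hypothesis | Endpoint or analysis that addresses it |
|---|---|
| Less opioid needed | Total opioid during the stay (primary) |
| Longer analgesia | None directly. Mean VAS, total opioid and the mixed model are indirect |

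The mixed model comes closest, but section 10(i) names no group-by-time contrast, scores are 4 hours apart, and the model adjusts for pain medication. Opioid use after the block is itself an outcome of how long the block lasts, so adjusting for it can remove part of the effect of interest.

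**2. The plan's own power figure**

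Inputs from section 10(i): difference 1.5, SD 2.0, 30 per group, two-sided 0.05, two-group t-test. Standardised difference = 1.5 / 2.0 = 0.75; noncentrality = 0.75 × √(30/2) = 2.905 on 58 degrees of freedom. Power is 81.5%, so the stated 81% reproduces. It applies to a 1.5-point difference in mean VAS, not to duration.

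**3. Dilution of a late benefit**

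Assumption: six 4-hourly scores (24 h, the usual inpatient time in section 10(e)), with a 1.5-point difference at w of the six and none at the others. Difference in means = 1.5 × w / 6. SD 2.0 is applied to the stay average, as in the plan's calculation.

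| w | Difference in means | Noncentrality | Power |
|---|---|---|---|
| 2 | 0.50 | 0.968 | 16% |
| 3 | 0.75 | 1.452 | 30% |
| 4 | 1.00 | 1.936 | 48% |
| 6 | 1.50 | 2.905 | 81.5% |

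Conversely, a whole-stay difference of 1.5 would need 1.5 × 6 / w = 4.5, 3.0 or 2.25 points at the affected times for w = 2, 3 or 4.

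**4. What time to first opioid could show with 60 patients**

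The documents give no distribution for this time, so the medians and censoring times here are assumptions. Log-rank power (Schoenfeld, 1:1) = Φ(√(D/4) × |ln HR| − 1.960), where D is the number of events.

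- If all 60 patients had an event, the ratio detectable with 80% power would be exp(−(1.960 + 0.842) × 2 / √60) = 0.485. With exponential times that is a median of 8 h against 8 / 0.485 = 16.5 h.
- Many patients would be discharged first. Events per arm = 30 × (1 − 0.5^(c / median)), with censoring at c hours.
  - c = 16: 22.5 + 14.7 = about 37 events, power about 60%.
  - c = 24: 26.3 + 19.1 = about 45 events, power about 68%.
- At HR 0.50 with control medians of 4 to 8 h and c = 24, about 46 to 56 events give 65% to 74%. At HR 0.60 even 60 events give only 51%.

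**The case against.** The strongest reply is that the plan is not silent on timing. VAS is taken every 4 hours and a mixed model over time is planned. The Background also cites a thoracic-surgery study reporting less pain at 8, 20 and 24 hours, which is precedent for reading the course of a block from serial scores. This stands in part: a reader might infer that the trial cannot address duration at all, and the documents do not support that. They support the narrower statement that the evidence is indirect and the relevant contrast is unspecified.

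The proposed endpoint has limits of its own, and these objections also stand:

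- It does not separate a longer block from a denser one. Section 10(g) ties tablets to moderate or severe pain scores, so a denser block also delays the first dose.
- Section 13 has the allocation disclosed to all staff caring for the patient. Only the patient is blinded, and staff who know the arm give the as-needed doses.
- The block is placed before surgery, so a clock started at the block counts operating time as analgesia.
- A reader might infer that dose timestamps are already in the study data. Section 10(g) says only that administration is captured, and section 10(i) speaks of quantities (pills or mg). Recorded times are a reasonable inference, to be confirmed; block time is not listed as a captured item.
- A reader might infer that 60 patients give 80% power for medians of 8 h against 16.5 h. That needs an event in every patient, which conflicts with censoring at 16 to 24 h.

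The dilution pattern is also chosen, not derived: the documents give stays of 16 and 18 h (planning values), 23 h and 24 h, and do not say when a benefit would appear. That is why a range is shown.

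**Conclusion.** The mismatch holds. Duration of analgesia is half of the hypothesis, and no listed endpoint or planned analysis measures it directly. The opioid-need half is covered by a primary endpoint, so the gap concerns duration only, and the trial remains interpretable for pain and opioid use.

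Under the stated assumption that a 1.5-point benefit is confined to 2 to 4 of six scores, power on the stay mean falls from 81.5% to between 16% and 48%. This rests on SD 2.0 applying to the stay average; the plan does not say whether that figure describes a single score or an average, and a smaller SD for the average would give higher power. The objections limit how much weight time to first opioid can carry. They make it supportive estimation, but they do not remove the gap.

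**What to change.** Add time to first postoperative opioid dose as a named key secondary endpoint for the duration objective, and prespecify:

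- the source: Epic medication administration records, after confirming that block and dose times can be extracted;
- the time origin, given that the block precedes surgery;
- which opioids count as the first postoperative dose;
- censoring at discharge;
- the analysis: Kaplan-Meier curves and a log-rank test, with a hazard ratio and confidence interval.

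Beside it, report the group-by-time contrast in 4-hourly VAS from a mixed model that is not adjusted for postoperative opioid use.

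State in the plan that this endpoint is supportive: the sample was not sized for it, it reflects block density as well as duration, and dosing is by staff who know the arm.

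The cost is plan wording and work on the Epic extract, which is still being developed. It needs no new patients, visits or procedures and leaves the primary comparisons unchanged. It adds one secondary comparison.

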### 6) Background

## Enhanced pain control after reduction mammoplasty with bupivacaine and dexamethasone regional block

Breast reduction is among the most common procedures performed by the Plastic Surgery division at Temple University Hospital. These patients are generally admitted for 23 hour observation primarily due to significant postoperative pain. Currently regional nerve block is routinely performed with bupivacaine infiltration. This provides effective immediate postoperative pain control but is limited by the 2 to 8 hour duration of action provided by this drug. These patients typically require significant amount of narcotic analgesia in the postoperative period. Exparel® (bupivacaine liposome injection) is a commercially available long acting formulation of bupivacaine however its significant cost has been deemed prohibitively high for use at this and most other institutions.

A number of studies in the anesthesia literature have demonstrated that addition of dexamethasone to bupivacaine when administered as a perineural block extends the duration of analgesia. In Bjorn, et al. (Reg Anesth Pain Med, 2016 Dec) saphenous nerve block with 10mL 0.5% bupivacaine + 1mL 0.4% dexamethasone after ankle surgery significantly extended the time to first narcotic request compared to control with bupivacaine alone. Maher, et al. (Pain Med, 2016 Jul) examine the use of both IV dexamethasone (8mg) and combination perineural dexamethasone and bupivacaine as intercostal nerve block during VATS. They demonstrate statistically significant decrease in pain at 8, 20, and 24 hours postoperatively. Other studies have obtained similar results in a variety of orthopedic and neurosurgical procedures.

A PubMed search using terms “dexamethasone” and “nerve block” did not return any studies that pertain to plastic reconstructive surgeries including but not limited to breast reduction. Additionally, searches using “breast reduction” and “nerve block” or “mammoplasty” and “nerve block” returned only 1 relevant study that examines the use of Exparel® nerve block during mastectomy (Abdelsattar 2016). Again, no studies examine methods of prolonging the duration of regional anesthesia after reduction mammoplasty

### **7) Setting of the Human Research**

This study will be performed exclusively at Temple University Hospital. Patients will initially be identified and recruited during the preoperative clinic visit. The study will again be described to the subjects and consent obtained in the preoperative holding area prior to the procedure.

### **8) Resources Available to Conduct the Human Research**

The Plastic Surgery division at Temple University Hospital performs an average of 10 breast reduction mammoplasty procedures per

## Enhanced pain control after reduction mammoplasty with bupivacaine and dexamethasone regional block

month. We anticipate that the vast majority of these patients will be eligible for study enrollment and will agree to participate in the study due to the potential for improved pain control

Data collection is expected to occur over a period of 12 months. Much of this will be collected automatically from Epic patient data. With the assistance of the medical informatics department, an automated data collection framework is being developed.

This study will be led by [name] of the Plastic and Reconstructive Surgery Division and [name] from the Department of Anesthesia. [name] is an experienced researcher with multiple publications in the field of plastic surgery. He has a specific research interest in pain control. [name] is a specialist in pain medicine. He completed a fellowship in pain medicine at the University of Pennsylvania. He has book chapters and publications in the field of pain medicine.

Research Support will be provided by plastic surgery and general surgery residents. Total project staff is expected to total at least 5 people. We expect this to be more than adequate to conduct this research

Enrolled subjects will be admitted patients at Temple University Hospital. They will have access to all of the medical and psychosocial services provided to patients of the hospital in the event of an adverse outcome as a result of participation in this study

All persons involved in conducting this study will be fully briefed on the background and protocol by the primary investigator or study coordinator prior to any involvement with the study. There will be ongoing oversight by the PI and study coordinator of all study subjects and personnel.

### **9) Prior Approvals**

No prior approvals are required. The Division of Plastic and Reconstructive Surgery and the Department of Anesthesia have approved this study.

### **10) Study Design**

#### **a) Recruitment Methods**

Research subjects will be identified in the plastic surgery clinic when they are scheduled for breast reduction surgery. The study

## Enhanced pain control after reduction mammoplasty with bupivacaine and dexamethasone regional block

will be described to patients when they agree to surgery. They will again be briefed on the study on the day of surgery. No additional recruitment methods will be required. No compensation will be provided to study participants.

### **b) Inclusion and Exclusion Criteria**

Initial in office screening will easily identify all patients who are requesting and scheduling breast reduction surgery. Criteria to be included in the study are women aged 18-80 undergoing elective bilateral breast surgery with ASA class 1-3.

Exclusion criteria are allergy to any of the study medications, history of chronic pain condition or narcotic dependency, history of chronic renal or hepatic disease, history of diabetes mellitus, and history of previous post operative nausea and vomiting. Prisoners and pregnant patients will also be excluded. Screening for appropriate subjects will occur in the clinic. ASA determination will be made by the anesthesia department during preoperative testing.

### **c) Local Number of Subjects**

An average of 10 breast reductions are performed monthly at Temple University Hospital. We expect nearly all of these patients to meet screening criteria and to agree to participate in this study

### **d) Study-Wide Number of Subjects**

This is a single site study. Anticipated number of subjects is approximately 60

### **e) Study Timelines**

- Data collection will occur over a period of 12 months
- [Interim analysis will be conducted by an independent at 6 months to confirm the quality of the data](#)
- Patient participation is limited to the length of the hospitalization for breast reduction procedure plus the first postoperative visit. For most subjects this will be 24 hours as inpatients with the postoperative visit occurring 1 week after surgery.

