## Enhanced pain control after reduction mammoplasty with bupivacaine and dexamethasone regional block

life survey scores at the first post-operative visit. . Patient participation is concluded following the first post-operative visit

Patient participation will be terminated if any adverse reaction to the study medication is noted.

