### **11) Risks to Subjects**

Regional nerve block is an optional component of the standardly performed breast reduction at this institution. Participation in the study does entail all the standard risks of this procedure. These are primarily bleeding or bruising at the injection site, nerve damage resulting in pain, numbness or weakness, infection, and

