## Enhanced pain control after reduction mammoplasty with bupivacaine and dexamethasone regional block

inadvertent systemic injection of the anesthetic. There is a very small risk of pneumothorax.

Primary additional risk to subjects compared to the standardly practiced block is allergic or adverse reaction to the study medication posed by the administration of dexamethasone. Adverse effects of this medication include behavioral disturbance, cardiac arrhythmia, hyperglycemia, and immune suppression. There is additional risk of increased postoperative pain due to deviation from standard nerve block procedure.

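### Infection, nerve damage and immune suppression are named risks, but the plan has no systematic way of finding them and no planned data collection after about 1 week

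*Combined protocol and SAP*

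**What the plan says.** **Named risks (Section 11).** The standard risks of the block, which both arms receive, include "nerve damage resulting in pain, numbness or weakness, infection, and" accidental systemic injection. Dexamethasone is described as the main added risk: "Adverse effects of this medication include behavioral disturbance, cardiac arrhythmia, hyperglycemia, and immune suppression".

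**Length of follow-up (10(e) and 10(f)).** "Patient participation is limited to the length of the hospitalization for breast reduction procedure plus the first postoperative visit". The timing is given as: "For most subjects this will be 24 hours as inpatients with the postoperative visit occurring 1 week after surgery". Section 10(f) repeats the end point: "Patient participation is concluded following the first post-operative visit". It adds: "Patient participation will be terminated if any adverse reaction to the study medication is noted".

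**Data at the last visit (10(g)).** "Patients will be asked to complete the MD Anderson Brief Pain Inventory Short Form and both the Breast-Q or the SF-36 questionnaire". No wound, infection, numbness or weakness item is listed, and no endpoint in 10(f) is a safety endpoint.

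**Adverse events (10(k)).** The principal investigator evaluates events linked to study medication, and a MIDAS report is filed for any adverse event. If events occur, an interim summary goes to the IRB at 1 month. The study stops if the interventions lead to intensive care or death.

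**Knowledge of allocation (Section 13).** Patients are blinded. All staff caring for them in hospital are told the arm.

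**The concern.** A protocol that names specific harms of the block and of the added drug would be expected to say how it will look for them. Here the risk section and the data collection sections do not meet. The outcomes are built around a stay of about a day and a survey at about a week, and nothing in the schedule asks every patient about infection or new numbness or weakness.

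At stake is how the safety side of the report can be read. If the trial finds better analgesia with dexamethasone and has few or no infections or nerve symptoms on file, a reader cannot tell whether few occurred or few were noticed. Because treating staff know the arm, what is noticed and attributed to study medication could also differ between arms, even though the visit schedule is the same in both.

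**Working it through.** The plan gives no figure on this point to reproduce, so the sections are set side by side first. Some arithmetic on precision follows.

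**1. Each named risk against what is collected**

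| Risk in Section 11 | Scheduled study item | Fallback in 10(k) |
|---|---|---|
| Nerve damage: pain | Brief Pain Inventory at about 1 week | Reporting if noticed |
| Nerve damage: numbness or weakness | None listed | Reporting if noticed |
| Infection | None listed | Reporting if noticed |
| Immune suppression | None listed | Reporting if noticed |

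Pain is therefore covered at the visit. The other rows are not.

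**2. What 10(k) does and does not supply**
- It supplies a reporting route, a stopping condition and one summary.
- It gives no method, definitions, schedule or window for finding events.
- Investigator evaluation is confined to events linked to study medication. An infection or nerve symptom put down to the needle or the surgery may fall outside it, although the MIDAS requirement covers any adverse event.
- The 1-month summary has no stated starting point (study start, first patient, or each patient's surgery). It cannot be read as 30-day follow-up of each patient.
- Under 10(f), an adverse reaction to study medication ends participation. No further data collection on that patient is described.

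**3. What systematic capture would give at the planned size**

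Input: 30 per group, 60 in total (10(i) and 10(d)). With zero events in n patients, all of whom were assessed, the one-sided 95% upper limit is 1 − 0.05^(1/n).
- n = 30: 1 − 0.05^(1/30) = 9.5%
- n = 60: 1 − 0.05^(1/60) = 4.9%

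These limits hold only if every patient was assessed. If just a share s of events is noticed, zero reports bound s × risk, so the limit on the risk itself is 9.5%/s. With an assumed s of 50% it is 9.5%/0.5 = 19%. Under 10(k) s is unknown and could differ by arm, so no limit can be stated.

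**4. What it would not give**

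Take 5% versus 15% as an assumed contrast, with 30 per arm and two-sided 0.05 (normal approximation, pooled variance under the null):

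Φ[(0.10 − 1.96 × √(2 × 0.10 × 0.90/30)) / √((0.05 × 0.95 + 0.15 × 0.85)/30)] = Φ[(0.10 − 0.1518)/0.0764] = Φ(−0.68) ≈ 25% power.

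The data would be descriptive even with complete capture.

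**5. Illustration of late events (assumed rates)**

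The documents give neither event risk nor timing. Suppose 25% to 75% of events arise by the 1-week visit, so 75% to 25% fall after it.

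| Assumed risk | Expected events in 60 | Expected after the visit |
|---|---|---|
| 2% | 60 × 0.02 = 1.2 | 0.3 to 0.9 |
| 5% | 60 × 0.05 = 3 | 0.75 to 2.25 |
| 10% | 60 × 0.10 = 6 | 1.5 to 4.5 |

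A sizeable part of a small count could fall outside the study data, but the number depends entirely on the assumptions.

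**The case against.** The strongest reply is that 10(k) exists. A reader might infer from 10(e) and 10(g) that these harms are not assessed at all. The documents do not support that: 10(k) provides investigator evaluation and MIDAS reporting, and sets no cut-off at the first visit. An infection or numb area noticed in hospital or at the visit has somewhere to go. This stands, and it limits the point to the absence of systematic, scheduled ascertainment.

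Three further replies stand in part.
- **Scope.** The objective and endpoints concern analgesia, opioid and antiemetic use, length of stay and survey scores. It would be speculation to say that the trial will declare no excess of harm. The narrower statement remains: it would have no basis for a statement either way beyond about 1 week.
- **Which infection.** In Section 11 infection appears among the risks of the block. Surgical wound infection is not named, and its link to the trial runs only through immune suppression. A definite number of missed wound infections is therefore not supported.
- **Power.** Sixty patients cannot test a difference in rare harms. True, but that argues for descriptive reporting, not for leaving the data uncollected.

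On allocation, Section 13 speaks of staff caring for the patient in hospital. It does not say who sees the patient at the first visit or what they know. Differential reporting is thus a possibility, not an established bias.

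**Conclusion.** The point holds in this form: infection, nerve damage and immune suppression are named as risks, no systematic assessment of them is planned, and no study data collection is planned after the visit at about 1 week. Section 10(k) relies on unscheduled reporting, and treating hospital staff know the arm.

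The efficacy results are not affected. The loss is in interpretation of harm: few or no reported events could not be turned into a bound on risk, whereas assessing every patient would give an upper limit of 9.5% per arm for zero events in 30. The illustrative late-event counts rest on assumed rates and should not be quoted as a finding about this trial.

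A reader might also infer that patient identifiers would be destroyed too soon for a later chart extraction. They would not: 10(h) keeps the identifying file until all analyses are complete. The change is worth making because it is cheap, but it does not threaten the main analysis.

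**What to change.** Amend 10(e), 10(g) and 10(k) as follows.

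1. **First visit.** For every patient, record yes or no for wound or injection-site infection, wound breakdown, and new numbness or weakness, regardless of judged relation to study medication.
2. **Later extraction.** Make one Epic extraction per patient at a fixed time after surgery, such as 30 days. Capture antibiotics, re-visits, readmission or reoperation for infection or wound problems, and any persisting nerve symptoms noted. The 30 days is a suggestion; no figure in the documents fixes it.
3. **Participation ended early.** State whether these items are still collected, with consent, from patients whose participation ends under 10(f) or who are withdrawn under 10(l).
4. **Summary timing.** Give the starting point of the 1-month summary in 10(k).
5. **Reporting.** Present counts by arm with exact confidence intervals, labelled descriptive, and state the 9.5% upper limit for zero events in 30.

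**Cost.** The change needs protocol and consent wording, a short form at a visit already held, and one query on the Epic extraction already being developed. There is no extra visit or procedure, and no change to 10(h). With a 30-day extraction, data collection for the last patient runs about 30 − 7 = 23 days longer. The remaining weakness is that care received at other institutions would be missed.
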